### **2.1 Primary Aim 1**

The primary objective is to compare the relationship between BMI-Z score and cardiometabolic risk factors in youth with DS, and in age-, sex-, race-, ethnicity- and BMI-Z score- matched controls.

a) Compare cardiometabolic risk factors [non-HDL cholesterol, lipoprotein subclass particles, blood pressure, insulin resistance (measured by HOMA-IR), insulin sensitivity index (ISI), glucose tolerance, inflammatory markers, and adipokines)] in adolescents with DS and in matched controls.

b) Determine the extent to which adiposity (fat mass by DXA) explains this relationship in DS vs. controls.

---

c) Assess cardiac end organ injury (pulse wave velocity (PWV) and left ventricular mass) in relationship to BMI-Z score in adolescents with DS and controls. Determine whether BMI-Z or other measures of adiposity (skin-fold thickness, waist circumference) better discriminates adolescents with DS at increased cardiometabolic risk.

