#### **4.1.1 Visit 1**

- Fasting Blood Sample: Will be completed by nursing staff. A total of approximately 12.5 mL (approximately 2½ teaspoons) of blood will be obtained from all participants. Subjects who do not undergo OGTT will be allowed to eat after the fasting blood sample.
- OGTT: A 2 hour OGTT will be done only in subjects with BMI  $\geq$ 85thtile, not known to have diabetes. A total of approximately 7.5 mL (1½ teaspoons) of blood will be obtained. The OGTT will be performed by nursing staff. A blood drawing IV will be placed. Baseline BG and insulin will be obtained. Subjects will ingest glucose solution (1.75 g/kg; maximum of 75 g) over 2 minutes. BG and insulin will be draw at 30, 60, 90, and 120 minutes via a blood drawing IV. For subjects refusing a blood drawing IV, BG and insulin will be drawn fasting and at 120 minutes. If a subject refuses the OGTT, only fasting labs will be obtained. Subjects who undergo OGTT will be allowed to eat after the OGTT is completed.
- Anthropometric Measurements: Performed by trained research anthropometrists, in order to assess body composition.

- 
- DXA Scan: The scan measures body composition and will be conducted and analyzed by trained staff.
  - Pubertal Status: Tanner staging of puberty will be performed by a pediatric endocrinologist team member. This exam will take place in a private exam room.
  - Pulse Wave Velocity (PWV) and Pulse Wave Analysis (PWA): The PWV and PWA will be performed by a trained technician
  - Echocardiography: Left ventricular mass will be measured by a trained sonographer and analyzed by the study cardiologist.
  - Family History of CVD, Dyslipidemia, T2DM: The study coordinator or appropriate member of the investigative team will administer a CRF to collect relevant patient medical history, family history of CVD/dyslipidemia/T2DM, sedentary and physical activity for each participant. Each question will be verbally communicated to the parent/participant, and the team member will show the questions as they are read, as appropriate.

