#### **5.1.4 Glucose Tolerance Test**

Glucose Tolerance (2-hour oral glucose tolerance test (OGTT)) will be performed by nursing staff. Subjects will be told to eat a high carbohydrate diet for 3 days before the study. Topical anesthetic ointment at the phlebotomy sites will be offered the morning of the visit. Baseline BG and insulin will be obtained. Subjects will ingest glucose solution (1.75 g/kg; maximum of 75 g) over 2 minutes. BG and insulin will be drawn at 30, 60, 90, and 120 min via a blood-drawing IV. However, the investigators realize that not all subjects will tolerate placement of the blood drawing IV, particularly given that children with Down syndrome may have developmental delays. For these subjects, BG and insulin will be drawn fasting, subjects will ingest glucose solution as described above, and a second blood draw will occur at 120 minutes. OGTT will be interpreted based on American Diabetes Association criteria: Fasting BG: <100 mg/dl = normal, 100-125mg/dl = impaired fasting glucose (IFG), ≥126 mg/dl = diabetes; 2-hour BG <140 mg/dL = normal, 140-199 mg/dL = impaired glucose tolerance (IGT), ≥200 mg/dL = diabetes.

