#### **5.1.8 Safety Evaluation**

The study investigators will be responsible for safety monitoring. A routine needle stick or an IV line used for drawing blood may cause some discomfort (topical anesthetic cream will be available), bruising, and rarely fainting. Use of the anesthetic cream may cause an allergic reaction. Although high adiposity is possible in participants with BMI < 85th percentile and might contribute to abnormal glucose tolerance, we will limit the subjects undergoing OGTT 1) to minimize participant burden in this cohort of children with developmental disabilities, and 2) on the likelihood of finding cardiometabolic abnormalities. We confined our IR assessment to HOMA-IR rather than IVGTT or clamp studies--considered the gold standard for IR assessment-- in the spirit of sensitivity to these children with intellectual disabilities and their families. We will obtain interim time points within the OGTT to calculate ISI, a measure of whole body insulin sensitivity. This requires a minimum of 5 time points, necessitating the placement of a blood-drawing IV. Given the children's developmental disabilities, some children may not tolerate this procedure—in this subset only time points 0 and 120 will be drawn and ISI omitted from their analyses.

Participants will be fasting 12 hours prior to their study visit. This may cause hunger pangs, upset stomach, headache, or light-headedness. If the participant shows any signs of clinical instability or definitively decides to discontinue participation, the study visit will be ended. Possible side effects of the OGTT include temporary high or low blood sugar. A risk of the OGTT includes an upset stomach. Participants will be monitored by a nurse or doctor during the study procedures. Episodes of low blood glucose will be treated with oral or IV glucose when indicated.

During the study visit, if a participant is found to have any previously unknown medical conditions, they will be referred to their pediatrician for care.

This protocol also involves exposure to radiation from the DXA scans. However, this involves a very small radiation exposure, which is unlikely to cause any untoward effects to the participant. Being that the protocol may be unsafe to an unborn child, pregnancy is an exclusion criterion of the study.

The noninvasive measures of arterial stiffness and central pulse pressure are done via Pulse Wave Velocity and Pulse Wave Analysis. This poses little risk to the patient.

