### **6.3 Potential Problems/Feasibility**

If we find no differences in CMR factors between youth with DS and controls, the resulting estimates (and confidence bounds) will still generate crucial information, given the literature claims of decreased CVD risk in DS, and scarcity of data on T2DM risk. Confidence bounds on estimates will allow us to rule out clinically important differences. We might find that DS children are at decreased CVD risk compared to unaffected controls. Such information would help guide clinicians caring for children with DS, and prevent unnecessary screening. Although high adiposity is possible in participants with BMI < 85th percentile and might contribute to abnormal glucose tolerance, we will limit the subjects undergoing OGTT 1) to minimize participant burden in this cohort of children with developmental disabilities, and 2) on the likelihood of finding cardiometabolic abnormalities. We confined our IR assessment to HOMA-IR rather than IVGTT or clamp studies--considered the gold standard for IR assessment-- in the spirit of sensitivity to these children with intellectual disabilities and their families. We will obtain interim time points within the OGTT to calculate ISI, a measure of whole body insulin sensitivity. This requires a minimum of 5 time points, necessitating the placement of a blood-drawing IV. Given the children's developmental disabilities, some children may not tolerate this procedure—in this subset only time points 0 and 120 will be drawn and ISI omitted from their analyses. Measures of LV mass may still be confounded by mild valve regurgitation or EKG conduction abnormalities. We are aware of this issue, and will interpret de-identified results with the expertise of the study cardiologist(s). They advocate acquiring this data, given the cardiometabolic implications of LV mass. The technique has not been used previously in this population and will generate novel data.

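### ISI is omitted for children without the blood-drawing IV, a loss the plan expects particularly in Down syndrome, and nothing checks whether that selection moves the DS–control ISI contrast

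*Combined protocol and SAP*

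**What the plan says.** Section 2.1 lists, among the Aim 1a factors to compare, "insulin resistance (measured by HOMA-IR), insulin sensitivity index (ISI), glucose tolerance, inflammatory markers, and adipokines)] in adolescents with DS and in matched controls". Section 6.1 fits a separate adjusted regression for each risk factor with DS as the exposure. Section 6.1.1 adds a DS by BMI-Z interaction, and section 6.1.2 adds fat mass.

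Sections 5.1.8 and 6.3 say that ISI needs at least five time points and therefore a blood-drawing IV. Both expect some failures: "Given the children's developmental disabilities, some children may not tolerate this procedure". Section 5.1.4 names the group: "not all subjects will tolerate placement of the blood drawing IV, particularly given that children with Down syndrome may have developmental delays". Both 5.1.8 and 6.3 then give the same rule: "in this subset only time points 0 and 120 will be drawn and ISI omitted from their analyses".

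Section 4.1.1 shows what remains: "For subjects refusing a blood drawing IV, BG and insulin will be drawn fasting and at 120 minutes". It adds a second route to missing ISI: "If a subject refuses the OGTT, only fasting labs will be obtained".

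No missing-data method appears in section 6. The propensity weights in 6.1 model the probability of DS, not of a complete OGTT. The sensitivity analysis there concerns unobserved confounders.

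**The concern.** The reason given for losing ISI, developmental disability, goes with the exposure being studied. Children with DS who contribute an ISI are those who tolerated an IV, while controls are expected to be largely complete. If tolerance is related to insulin sensitivity in a way the model covariates do not capture, the DS coefficient for ISI mixes the group difference with the selection.

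This matters most for a null result. Section 6.3 intends to use confidence bounds to exclude clinically important differences and to help avoid unnecessary screening. Complete-case bounds for ISI make no allowance for selection, and the plan has no step that would show whether selection has acted.

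**Working it through.** **1. The plan's power figure.** Section 6.2 states power above 0.85 at 0.35 SD with 155 DS and 105 controls by a nonparametric test, and gives no figure for ISI. With Wilcoxon efficiency 3/π, power = Φ(0.35·√(3/π) / √(1/n₁ + 1/n₂) − z).
- 155 and 105: 0.342 / 0.1264 = 2.706. Two-sided 0.05 gives Φ(2.706 − 1.960) = 0.77; one-sided 0.05 gives Φ(2.706 − 1.645) = 0.86. The stated figure reproduces only one-sided; the plan gives neither alpha nor sidedness.

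**2. The ISI set.** Section 6.1.1 estimates that 50% of DS subjects will reach the BMI threshold for an OGTT: 155 × 0.5 ≈ 78. Applying the same share to BMI-Z-matched controls is an assumption: 105 × 0.5 = 52.5, so 52 or 53.
- 78 and 52: 0.342 / 0.1790 = 1.910; two-sided power Φ(−0.050) = 0.48.
- 20% DS loss (assumed), 62 and 52: 0.342 / 0.1880 = 1.819; power Φ(−0.141) = 0.44.
- 40% DS loss (assumed), 46 and 52: power 0.39.

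Most of the fall from 0.77 comes from the BMI restriction, not from IV failure.

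**3. Bias in unadjusted means.** Let m be the share of DS children in the OGTT set who lack ISI, and d the tolerant-minus-intolerant gap in SD, with no control loss. The bias is m × d. Neither quantity is in the documents.
- m = 0.20: 0.05 SD at d = 0.25, 0.10 at d = 0.5, 0.20 at d = 1.0.
- m = 0.40: 0.10, 0.20 and 0.40 SD.
- d = 0: no bias.

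**4. Bias in the kind of model planned.** The plan adjusts for covariates, so step 3 is not the relevant size. The simulation regressed ISI on DS, an adiposity measure and their interaction. Assumed inputs: 78 DS, 53 controls, true difference −0.35 SD, ISI–adiposity correlation −0.6, about 29% DS and 7% control loss, log-odds 0.7 per SD where loss depends on ISI, and a 0/120 minute proxy correlated 0.8 with ISI.

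| What drives the loss | Adjusted complete-case | Multiple imputation with DS × adiposity |
|---|---|---|
| Low ISI more often lost | −0.25 (error +0.10) | −0.30 (error +0.05) |
| High ISI more often lost | −0.44 (error −0.09) | −0.39 (error −0.04) |
| Adiposity only | no bias | no bias, slightly more precise |
| Random within group | no bias | no bias, slightly more precise |

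Adjustment matters. When low ISI is lost, the raw complete-case difference is −0.22. When loss depends on adiposity alone, the raw difference is −0.26 but the adjusted one returns to −0.35.

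**5. The interaction must be in the imputation model.** With an assumed true DS × BMI-Z interaction of −0.40, imputing without that term gave about −0.37 (random loss within group) and −0.36 (adiposity-driven loss). Complete-case gave −0.40 in both.

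**The case against.** A reader might infer that the values collected from these children are wasted. The documents do not support that. Fasting glucose and insulin give HOMA-IR, fasting and 2-hour glucose give the glucose-tolerance categories compared in 6.1.1, BMI-Z is in the Aim 1a models, and fat mass enters in Aim 1b. What remains is narrower: none of this is used to recover or check ISI, and 2-hour insulin has no named use.

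A reader might also infer that the ISI contrast is biased. That does not follow. The documents attribute intolerance to developmental disability and never to insulin sensitivity. If loss depends only on variables in a correctly specified model, complete-case regression is unbiased, as step 4 shows. Differential selection is what the plan expects; bias is only possible.

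Nor is the main conclusion at risk. Section 6.2 names non-HDL cholesterol as the primary CMR outcome measure, and HOMA-IR needs only a fasting sample. The plan also discloses the omission, and two samples cannot yield a five-point ISI directly.

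These objections stand. They rule out calling the contrast invalid, and they rule out replacing the complete-case analysis with imputation, which has its own model dependence (step 5). They do not answer the remaining point: the plan expects loss that differs by group and specifies no count, comparison or sensitivity analysis for it.

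**Conclusion.** The point holds as a cheap improvement. The omission rule makes the ISI comparison and the DS × BMI-Z model for ISI complete-case analyses on a set selected differently by group, with no check. Bias arises only if tolerance relates to insulin sensitivity beyond the model covariates. Under the assumptions in step 4 it is about 0.1 SD in either direction, against an effect of 0.35 SD; it is zero if there is no such relation. Using the 0 and 120 minute values roughly halves it but does not remove it when loss depends on ISI itself. Loss rates, selection strength, proxy correlation, adiposity correlation and the control OGTT share are all assumptions, so the size is illustrative. The extra loss of power from IV failure is small beside that from the BMI restriction.

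**What to change.** Keep the five-point ISI analysis. In sections 6.3 and 5.1.8, add to the sentence that omits ISI:

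1. Report the number with and without ISI by group, counting separately those with two samples and OGTT refusers with fasting labs only. Compare children with and without ISI on HOMA-IR, BMI-Z, fat mass and, where drawn, the 120 minute values.
2. Prespecify a multiple-imputation analysis of ISI from 0 and 120 minute glucose and insulin, DS, BMI-Z, DS × BMI-Z, fat mass, pubertal stage, age and sex, with fasting values only for OGTT refusers. Report it beside the complete-case result.
3. Compare DS and controls on an index computed from the 0 and 120 minute values in every OGTT subject. This needs no imputation model, though it is not the five-point ISI and does not cover refusers.
4. If these disagree with the complete-case result, do not use the complete-case ISI bounds to rule out a difference. Say in advance what counts as disagreement, for instance an imputed interval that includes a difference the complete-case interval excludes.

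The cost is a little more analysis work and, for item 2, reliance on an imputation model. No new samples or visits are needed.

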## **7 SAFETY MANAGEMENT**

### **7.1 Clinical Adverse Events**

Clinical adverse events (AEs) will be monitored throughout the study.

### **7.2 Adverse Event Reporting**

The Investigator is responsible for recording and reporting unanticipated problems related to research that occur during and after study treatment. The plan for Adverse Event reporting should be consistent with the study site IRB Guidelines. Since the study procedures are not greater than minimal risk, SAEs are not expected. If any unanticipated problems related to the research involving risks to subjects or others happen during the course of this study (including

---

SAEs) these will be reported to the IRB in accordance with the study site policies. AEs that are not serious but that are notable and could involve risks to subjects will be summarized in narrative or other format and submitted to the IRB at the time of continuing review.

### **7.3 Medical Emergencies (if applicable)**

The investigators do not anticipate any medical emergencies with this minimal risk study. However, there is a possibility that study participants may have low or high blood glucose or side effects resulting from the OGTT. The study participants will be monitored throughout testing. The study coordinator, a nurse or physician will be present during these procedures. If necessary, episodes of significant hypoglycemia will be treated immediately with oral or IV glucose (although unlikely).

## **8 STUDY ADMINISTRATION**

### **8.1 Data Collection and Management**

Data Management CHOP CTRC Informatics Core will create case report forms (CRF) and REDCap database for data capture. REDCap is an NIH-supported web-based data management software designed by Vanderbilt University investigators. Of special benefit to the proposed investigation is the interface between EPIC (the EMR) and the research database that allows for use of clinical information for research purposes. For data not already incorporated in EPIC, once the investigative team confirms complete and accurate data, it will be entered into REDCap. Using REDCap checking tools, the data manager confirms completeness and valid values weekly and informs any errors or omissions to the investigative team for prompt resolution. Real-time data checking ensures prompt creation of an analysis dataset upon data acquisition completion. Tables generated by REDCap will be exported and merged for use with Stata and SAS statistical packages as needed for immediate access to the research team.

The PI is responsible for the accuracy and completeness of data collection and management. The PI may designate qualified individual(s) to collect data and manage data. Only investigators and research staff that have completed appropriate IRB training and approval and are listed on the IRB approved protocol are eligible to collect and work on information from the study. Future studies that may use patients or data collected from this study must have separate approved IRB protocols and consent forms, if applicable.

Recruitment data will be recorded onto the screening questionnaire after the verbal consent is recorded. Original data will be recorded directly onto CRFs by the study coordinator or a study investigator. Copies of laboratory, physical exam, anthropometric, DXA, PWV, and PWA results will be received through inter-office mailing, picked up directly, and sometimes through email. This information also will be recorded onto CRFs while the originals may be kept at the testing site. CRFs will be kept in a locked filing cabinet in a locked room at all times. All information will be transferred to REDCap, a secure, web-based application supported by the CHOP Research Institute. The password to log onto the database will be unique to each member of the study team. CNMC study staff will be assigned to a REDcap user group that will restrict their access so they may view and edit solely the information of subjects enrolled at CNMC. The CNMC Principle Investigator will have access to view/edit data of all subjects.

---

Note that only limited PHI (date of visit, date of birth) is included in the REDcap database. CHOP will have read-write access for data collected at both sites. CHOP will require access to edit records for both sites because several evaluations will be analyzed at CHOP, and reports including data from both CHOP and CNMC sites will be forwarded to the CHOP team, who will then import or enter the data into REDCap. Written informed consent granting permission for other site(s) to access PHI will be obtained from all subjects. The CRF and REDCap database will be designed by the CTRC Informatics Services.

All data and records generated during this study will be kept confidential in accordance with institutional policies and on HIPPA subject privacy. The investigators/study team members/site personnel will not use such data and records for any purpose other than for conducting the study.

As a way to minimize the chance of PHI (protected health information) from being disclosed, a unique identification code will be used for each participant. The key to this code will be kept in a locked file in the PI/Study Coordinator's office.

If any publications result from this research, the participant will not be identified by name/PHI.

The information collected as part of this study will be kept for 6 years or until the completion of the study (whichever is longer). At that time, the information collected will be destroyed or all identifiable information will be removed. All keys will be destroyed at this time, as well.

## **8.2 Confidentiality**

All data and records generated during this study will be kept confidential in accordance with institutional policies and HIPPA's guidelines on subject privacy. The investigators/study personnel will not use such data and records for any purpose other than conducting the study.

## **8.3 Regulatory and Ethical Considerations**

### **8.3.1 Data and Safety Monitoring Plan**

Study progress and safety will be reviewed quarterly (and for frequently if needed) by the PI. Review of the rate of subject accrual, adherence to inclusion/exclusion criteria will occur quarterly to assure that participants meet the eligibility criteria. There will be ongoing collection of data on adverse events and compliance to the treatment protocol throughout the study by research staff, which will be reviewed monthly by the study team and PI. If there is an incidental finding deemed by the PI to be clinically relevant, the primary care provider will be notified. The parent/guardian will be notified and asked to follow up with the subject's primary care provider if during the visit; a subject is noted to have blood pressure that is  $\geq$  the 95th percentile for age, gender, and height. We will notify the parent/guardian/primary care provider with clinically relevant abnormal labs. Specifically, lipid levels/insulin levels/blood glucose levels/OGTT results/TSH and T4. Note that some labs, such as lipids and insulin, are run in batches and reporting of results may be delayed.

